$$\mathbf{Y}_0 = \beta_0 \text{ and } \mathbf{Y}_1 = \beta_0 + \beta_1 * \mathbf{Y}_1.$$

The fitted model has parameter estimates (β_0, β_1) and the associated covariance matrix $s_j^2 V_j$, where V_j is the usual $\mathbf{X}^T \mathbf{X}$ matrix from the intercept and variable \mathbf{Y}_1 .

For each imputation, new parameters (β_0^* , β_1^* ; and σ^{*2}) are drawn from a posterior predictive distribution of the missing data. The missing values of Y_j are then replaced with the predicted values using the following equation:

$$\beta_0^* + \beta_1^* * y_1 + z_i * \sigma^{*2}$$

where y_1 is the covariate value for the first variable and z_i a simulated standard normal deviate for the i^{th} individual.

The next step is to carry out the analysis of interest for each of the m imputed complete-observation datasets, storing the parameter vector and standard error estimates.

Finally, the results are combined using results from Rubin (1987) to calculate estimates of the within imputation and between imputation variability. These statistics account for the variability of the imputations and assuming that the imputation model is correct, provide consistent estimates of the parameters and their standard errors. The imputation model need not be exactly correct and the MI will provide these consistent estimates. The following are additional information and suggested code that can be used for MI:

In this appendix, we will assume that data are stored in a SAS dataset, with the following variables. Note that the variable names/labels are suggestions only and the actual names/labels and code levels should be consistent with current sponsor reporting standards.

SUBJID: subject identification number.

REGION and AGE_STRATA.

TRT: Treatment group (Placebo, Pregabalin 7.0 mg/kg/day, Pregabalin 14.0 mg/kg/day).

LN_BSZRT: A \log_e transformed baseline seizure rate $\log_e(\text{Baseline 24-hour seizure rate}_b + 1)$.

LN_SZRATE: A \log_e transformed double-blind seizure rate $\log_e(\text{Double blind 24-hour seizure rate}_t + 1)$.

IMPSTAT: Impstat = 1 if DC due to AE, death, or insufficient clinical response.
Impstat = 2 otherwise.

MISS: Miss = 1 if ln_szrate is missing. Miss = 0 otherwise.

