In order to impute missing data at the singular time point and based on the definition of the link function, first prepare an input dataset, making sure that it will contain only the intended donor and recipient patterns. Separate the input dataset <efficacy> into two datasets: IMP, containing all placebo subjects and those subjects from the pregabalin arms that have missing LN_SZRATE [Miss=1] and Impstat=1; and REST, containing the rest of the subjects from the pregabalin arms (those with non-missing LN_SZRATE [Miss=0] or Impstat=2).

title1 'Pattern Imputation based on reason for DC';

*these sets are exhaustive and mutually exclusive;

```
data IMP REST;
  set <efficacy>;
  if trt ne "Placebo" and (impstat = 2 or miss = 0) then output REST;
  if trt = "Placebo" or (impstat = 1 and miss = 1) then output IMP;
run;
```

Call PROC MI to impute missing data at the time point using dataset IMP as input.

*order of variables matters in proc mi;

```
proc mi data = IMP out = impout nimpute=100 seed = 233;
  class region age_strata;
  var region age_strata ln_bszrt ln_szrate;
  monotone regression(ln_szrate = ln_bszrt region age_strata);
run;
```

Call PROC MI to impute missing data at the time point using dataset REST as input.

*impute like randomized trt for active who are 'ignorably missing';

```
proc mi data = REST out = restout nimpute=100 seed = 238 ;
  class region age_strata trt ;
  var region age_strata trt ln_bszrt ln_szrate ;
  monotone regression(ln_szrate = trt ln_bszrt region age_strata) ;
run;
```

Assemble back a dataset containing all subjects.

*fully imputed integrated dataset;

```
data main ;
  set impout restout ;
run ;
proc sort data = main ;
  by _imputation_ trt ;
run ;
```

*Analysis of imputed data sets;

* Confirm the ordering of the trt variable for specifying the vector. Here it is assumed Placebo, Pregabalin 7.0 mg/kg/day, and Pregabalin 14.0 mg/kg/day ;

```
proc glm data=main;
  by _imputation_ ;
  class region age_strata trt ;
  model ln_szrate = trt region age_strata ln_bszrt ;
  lsmeans trt / diff=control('Placebo') tdiff pdiff cl;
  estimate 'Pregabalin 7.0 mg/kg/day vs Placebo' trt -1 1 0 ;
  estimate 'Pregabalin 14.0 mg/kg/day vs Placebo' trt -1 0 1 ;
  ods output lsmeans=lsm diffs=lsdiff estimates=estdiffs ;
run ;
```

quit ;

*integrated summary of results of imputed datasets, please note the degree of freedom (XXX) should come from MSE of GLM model above;

```
proc mianalyze parms(classvar=full)=lsm edf=XXX;

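### SAP Appendix 2.2.1: the dose contrasts assume a treatment order that the SAP's own labels do not sort into, and the printed imputation equation uses the variance where the SD belongs

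*SAP*

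**What the plan says.** All of this is in SAP Appendix 2.2.1 unless another place is named.

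- **Labels.** The treatment variable is listed as "TRT: Treatment group (Placebo, Pregabalin 7.0 mg/kg/day, Pregabalin 14.0 mg/kg/day". The appendix adds: "Note that the variable names/labels are suggestions only". It leaves the actual names and code levels to the sponsor's reporting standards and describes the code as suggested.
- **Type of variable.** The data step that splits the file compares `trt` with the text value Placebo, and the LS means line uses `control('Placebo')`. As written, the code needs `trt` to be a character variable.
- **Level order.** The comment above the model says "Confirm the ordering of the trt variable for specifying the vector" and continues "Here it is assumed Placebo, Pregabalin 7.0 mg/kg/day, and Pregabalin 14.0 mg/kg/day". The class statement is "class region age_strata trt", with no ORDER= option on the procedure. The data are sorted beforehand "by _imputation_ trt".
- **Contrasts.** These are "estimate 'Pregabalin 7.0 mg/kg/day vs Placebo' trt -1 1 0" and "estimate 'Pregabalin 14.0 mg/kg/day vs Placebo' trt -1 0 1". Their output is then pooled in PROC MIANALYZE by the typed contrast name. The least squares means are pooled separately, by treatment level.
- **Imputation equation.** The prose draws new regression coefficients and a new residual variance for each imputation. It replaces a missing value by the prediction plus a standard normal deviate times that variance. The code imputes with the monotone regression method of PROC MI.
- **Role.** SAP Sections 8.2.1 and 8.2.4 make this a sensitivity analysis in the ITT set. The primary analysis is the observed-case ANCOVA in the mITT set.

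**The concern.** A contrast vector is read against the order of the class levels, not against the text typed in its label. If the levels do not fall in the assumed order, the vector labelled 7.0 estimates another comparison. The order itself triggers no warning, because each vector still sums to zero and is estimable. The contrast output is what gets pooled, so a wrong label would carry through to the combined estimate, standard error and p-value.

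The equation raises a different worry. Scaling a standard normal deviate by a variance gives noise with the wrong spread unless the residual SD happens to be 1. Imputed values that are too little or too widely spread distort the pooled standard error.

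This is the only efficacy analysis in the ITT set, so it is the plan's check on missing data. It is likely to be run: SAP Section 7 triggers it when more than 5% of any treatment group lacks the post-baseline rate, and the sample size allowed for 10% discontinuation. It covers Level 2, which gates the step-wise procedure in SAP Section 4.2, as well as Level 1.

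**Working it through.** **Inputs from the documents.** SAP Table 1 gives planned differences of -0.668 (Level 2) and -0.448 (Level 1), SD 0.73, and groups of 44, 44 and 22. SAP Section 2.1 gives 10% discontinuation. SAP Appendix 2.1.1 gives -0.355 for Level 1 on the log(rate + 1) scale. The effects and the SD in Table 1 are adult values for the superseded constant 1/28. They are used here only to illustrate size.

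**Reproducing the plan's figures.** A two-sided two-sample t-test at 0.05 gives power 0.9321 for Level 2 and 0.8123 for Level 1. The SAP states 0.932 and 0.812. Also 110 / 0.90 = 122.2, which rounds up to the planned 123. The inputs are therefore read correctly.

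**Contrast order**

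1. A character sort of the three labels gives Placebo, Pregabalin 14.0 mg/kg/day, Pregabalin 7.0 mg/kg/day, because the character 1 precedes 7.
2. It is assumed, as standard software behaviour that the documents do not state, that without ORDER= the levels follow the sorted values. Ordering by data would give the same result, because the data are sorted by `trt` first.
3. Applying each vector to the planning effects, with placebo at 0:

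| Contrast label | Vector | Order assumed in the SAP | Sorted order of the labels |
|---|---|---|---|
| 7.0 vs Placebo | -1 1 0 | -0.448 (7.0) | -0.668 (14.0) |
| 14.0 vs Placebo | -1 0 1 | -0.668 (14.0) | -0.448 (7.0) |

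Each label would be wrong by 0.668 - 0.448 = 0.22. The precision changes places too. At SD 0.73 and the planned group sizes, the standard error is 0.73 × √(1/44 + 1/44) = 0.156 for Level 1 and 0.73 × √(1/44 + 1/22) = 0.191 for Level 2.

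**Noise term.** The correct term is z × σ\*, with SD σ\*. The printed term is z × σ\*², with SD σ\*². The ratio of printed to correct SD is σ\* itself.

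| Residual SD (assumed) | SD of printed noise | Error in the noise SD |
|---|---|---|
| 0.73 | 0.533 | 27% too small |
| 1.00 | 1.00 | none |
| 1.20 | 1.44 | 20% too large |

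The documents give no residual SD on the log(rate + 1) scale. A rough lower bound follows from the re-estimation formula, if the increase to about 150 means that the recalculated total reached 150. Then n\* = 150 / 2.5 = 60 per group and N_G = 120, so N = 120 - 1.96²/2 = 118.1. The SD is at least √(118.1 × 0.355² / (4 × (1.96 + 0.84)²)) ≈ 0.69. If the 150 already contains 10% dropout, 135 evaluable subjects give about 0.65. No upper bound follows, so both sides of 1 are shown.

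**Effect on the pooled standard error if the equation were hand-coded.** The simulation used 60/60/30 subjects, 100 imputations and 400 replicates. Data were missing completely at random, and imputation used baseline and treatment. The Level 2 effect (-0.5) and the baseline slope (0.8) were assumed. It leaves out region, age stratum and the code's placebo-based handling of some dropouts. For Level 1 versus placebo:

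| Residual SD | Missing | SE with σ\* | SE with σ\*² | Ratio |
|---|---|---|---|---|
| 0.73 | 10% | 0.141 | 0.135 | 0.96 |
| 0.73 | 20% | 0.150 | 0.138 | 0.91 |
| 1.20 | 10% | 0.233 | 0.244 | 1.05 |
| 1.20 | 20% | 0.248 | 0.268 | 1.08 |

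The 20% rows are an assumption. The plan allows for 10%.

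**The case against.** The SAP does not hide the ordering problem. It states the order it assumes, directly above the contrasts, and tells the programmer to confirm it. It calls the labels suggestions, and the listing is a template with placeholders for the dataset name and the degrees of freedom, so it cannot be run unedited. A swap needs three things together: the listed labels, default ordering and a missed check. Even then the pooled least squares means keep their true level names. SAP Section 8.2.4 asks for them beside the differences, so an attentive reader of the output could see the conflict. All of this stands. It limits the likelihood and reach of the error, but it does not make the vectors right: with the SAP's own labels, the check it asks for fails.

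On the equation, the supplied code leaves the residual draw to PROC MI and never uses the printed formula. That also stands. The formula is still wrong, and nothing in the SAP flags it. Because the code is only suggested, the prose remains the stated method for anyone who programs it another way.

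A reader might infer that the planned analysis will exchange all the dose results unnoticed, or that the planned imputations already carry the wrong noise. The documents support neither reading, for the reasons just given.

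**Conclusion.** Two defects stand in the current text, both limited in reach.

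- **Contrasts.** The assumed order contradicts the sort order of the listed labels. With those labels, default ordering and a missed check, the pooled contrasts of the ITT sensitivity analysis carry each other's dose names. On the planning effects the error is 0.22 per label. That figure is illustrative, because no Level 2 difference is given on the log(rate + 1) scale. The pooled least squares means are correctly named.
- **Equation.** The multiplier should be σ\*. The supplied code is not affected. If the equation were hand-coded, with 10% missing, the pooled standard error would be about 4% too small at SD 0.73 and about 5% too large at SD 1.2. The direction turns at SD 1, so it would be wrong to say that the intervals are always too narrow.

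A reader might also infer that the trial's main conclusion is at risk. It is not: the primary ANCOVA and its step-wise test use neither the contrast code nor the equation. The finding assumes standard default ordering and standard PROC MI behaviour. It merits correction because the contrast error would fall on the plan's only ITT check and costs almost nothing to remove.

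**What to change.** - With the SAP's labels, write `trt -1 0 1` for 7.0 versus placebo and `trt -1 1 0` for 14.0 versus placebo. Correct the order stated in the comment to Placebo, 14.0, 7.0. This is the most contained repair.
- If `trt` is coded numerically in dose order with ORDER=INTERNAL instead, keep the present vectors. The two tests of `trt` against the text value Placebo, and `control('Placebo')`, must then change as well. Otherwise observed placebo records would go to the wrong dataset and leave the placebo-based imputation without donors.
- As a check in either case, compare each pooled contrast with the difference between the pooled least squares means of that dose and placebo. In this additive model the two must agree.
- Replace σ\*² by σ\* in the noise term of the prose equation.

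The cost is a few lines in one SAP appendix. Data collection, patients, the sample size and the primary analysis are not touched.

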Appendix 2.2.2. Analysis Strategy Using a Poisson Model

Poisson Distributions often arise from a Counting process

- Seizure counts as a random variable Y
The expected value of the seizure counts is $E(Y) = \mu$
The variance of the seizure counts is $\text{Var}(Y) = \mu$

Generalized Linear Model for Seizure Counts with equal duration

- $g(\mu) = \ln(\mu) = \alpha + X\beta$
Distribution is Poisson
Link function $g(\mu)$ is the natural log
In other words $\mu = \exp(\alpha + X\beta)$

Incorporating exposure/V-EEG monitoring time (T) in the Model

- Off-setting the exposure/V-EEG monitoring time by $\ln(T)$
- $\ln(\mu/T) = \alpha + X\beta$
- $\mu = T \cdot \exp(\alpha + X\beta)$
- Adjust for unequal exposure/V-EEG monitoring times among treatment groups

Exposure/V-EEG monitoring time, T, is based on observed V-EEG monitoring time (evaluable hours).

If the ‘Criteria For Assessing Goodness Of Fit’ section of the output indicates that the value/df for both deviance and Pearson Chi-Square statistics is numerically much higher than 1 (ie, value/df > 1.5), then Poisson model is not quite adequate to describe the counts of seizures. This lack of fit is termed over-dispersion, and it indicates that the data contains more variability than what the model is explaining. While the maximum likelihood estimators for the fixed effect from the Poisson model are still consistent when over-dispersion is present, the variance is biased downward. Thus, statistical tests may lead to higher type I error rates (ie, p-values are smaller than what they should be) if over-dispersion was not present.

If over-dispersion is determined based on the threshold criteria above, a common statistical strategy of fitting quasi-likelihood and negative binomial models will be employed. A scale parameter (Scale=deviance, the dispersion parameter is estimated by the deviance divided by its degrees of freedom) will be specified to fit the overdispersed Poisson and negative binomial distributions, if warranted.

Appendix 2.2.3. Pooling

Pooling of sites will be determined prior to unblinding of the study. Any investigator center having less than 2 subjects in any given treatment group or efficacy outcome category within each strata will be defined as a ‘small’ center. The pooling of small centers will be based on the total number of subjects randomized at each center. Small centers will be pooled to large centers within the same country. When there are only small centers within a given country, small centers will be pooled to large centers within the same region.
